Our study period will extend 11 years (January 2004 to December 2014), a period of rapid growth of HDHPs,²² capturing an unprecedented sample size of patients with bipolar disorder transitioning to HDHPs. The intervention cohorts will include individuals who transitioned to HDHPs between January 2005 (after a minimum one year baseline period in a traditional plan) and December 2013 (to allow one year of follow-up). We will follow all subjects for 1 year before and 1 year after the index month of switching (*Figure 3*). Matched controls will be drawn from employers who chose to remain in a traditional plan in the same calendar year, and our matching approach will ensure calendar month of switch is also balanced across the study groups. We will require continuous enrollment for the 24 month study period for both groups.

Figure 3. Study design of HDHP members and controls

* A subgroup of members are “forced switchers” whose employers mandate that they transition from a traditional to a high-deductible health plan

C.5 Study Population for Aims 1-3 [RQ-3; CI-1 to CI-4; HT-1 to HT-4]: Inclusion Criteria: We will include health plan members aged 12 to 64 years at the beginning of the baseline period. Consistent with prior research,⁸⁹⁻⁹¹ we will use medical claims data and a validated algorithm^{36,41,43-45,92,93} to identify members who had at least two ambulatory encounters or one hospital encounter with a diagnosis of bipolar disorder (ICD-9 diagnostic codes: bipolar-I: 296.0, 296.1, 296.4-296.7; bipolar-II: 296.89; and bipolar-other: 301.11 and 301.13^{43-45,89-91}). The first advisory panel committee meeting in October 2015 directly shaped our cohort definition stream of work; advisors agreed that bipolar inclusion criteria should include requiring at least 1 inpatient or 2 outpatient diagnoses, to better ensure that the diagnosis is valid and relevant to the planned analyses. Despite the tightening of our diagnostic criteria, our newest cohort totals remain on target with the estimates in our original power analysis. Eligibility for the study is predicated on the principal diagnosis of bipolar disorder (any diagnosis) not just diagnosis at the first position, as advised by our stakeholder panel. The study cohort was derived through applying the following inclusion rules, therefore defining individuals as eligible for our study:

[name]

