Study cohort: Of 41,638,597 members enrolled in the national insurer during 2004-2012, we found 18,184,556 have a 2-year enrollment span, a study inclusion criterion. Among these, 148,706 have at least 1 inpatient or 2 outpatient diagnoses of bipolar disorder; this reflects a prevalence of 1% members with bipolar disorder, which is consistent with expectation among the commercially insured population. Among 148,706 members with bipolar disorder, 57,028 matched our age criterion (12 to 64 years of age). (We will conduct sensitivity analyses of our main results varying our bipolar diagnosis criteria [e.g., requiring diagnosis prior to index date, requiring only one diagnosis; [CI-5](#)]) To minimize selection bias, our study cohorts will include individuals whose employers offer only a single benefit type with no choice. Our intervention cohorts will include traditional plan members with bipolar illness who experience an employer-mandated switch to HSA-eligible HDHPs with full drug cost-sharing (i.e., out-of-pocket medications payments until the deductible limit is reached), or to HSA-ineligible HDHPs that subject medications only to copayments as in traditional health plans. The control cohort will include members with bipolar illness whose employers offered only a traditional plan for the follow-up year. We estimate that 7,227 have HDHP insurance and 49,801 have traditional plan insurance. **Exclusion Criteria:** We will exclude members age 65 years or older who could be eligible for Medicare benefits, including drug coverage through Medicare Part D. We will also exclude members whose employer offered a choice of health plan. This strengthens our design by reducing potential selection bias due to, for example, healthier members selecting HDHPs or individuals anticipating discretionary utilization. . Input from our panel advisory meetings led to the decision to exclude from our cohort those individuals with a diagnosis of schizoaffective disorder or schizophrenia in order to identify a clinically homogenous group for our study, as advised by our clinical psychiatrist co-investigator [name]. This criterion was further supported by our advisors at DBSA. According to sources at DBSA, schizophrenia and schizoaffective disorder are not comorbidities seen in their peer population. In their judgment, people living with schizophrenia and schizoaffective disorder are unlikely to come to DBSA meetings and would have their needs better met in other settings. The ineligibility criteria therefore included the 3 categories: 1) patients with only 1 outpatient bipolar diagnosis, 2) 1 inpatient or 2 outpatient diagnosis of schizophrenia diagnosis, and 3) 1 inpatient or 2 outpatient diagnosis of schizoaffective disorder. We estimate 3,731 individuals were excluded from the study cohort due to evidence of schizoaffective disorder and schizophrenia. There have been no changes in identifying eligible individuals to enroll in our approved research plan beyond the stakeholder advisory panel decision to exclude schizoaffective disorder and schizophrenia, calculate their overlap with the bipolar population, and exclude them from the final cohort.

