C.10 Sample Size Estimates and Power Calculations [HT-1 to HT-4]: Using 10 years of data (2003-2012), we found 42 million unique adolescents and adults aged 12-64, approximately 450,000 of whom (~1%) had at least one bipolar disorder diagnosis. This is consistent with our expectation of a lower disease prevalence among commercially-insured adults compared with the 3% prevalence estimated by epidemiological surveys,³ because individuals with bipolar disorder less commonly have private insurance.¹³¹ A total of 109,012 of the 450,000 with a bipolar diagnosis met our inclusion criteria of 2 years continuous enrollment, with the first year in a traditional plan, the second in a traditional or HDHP, and no choice from the employer at any point regarding plan type. Projecting to 2014, our sample will include over 10,800 HDHP members (1525 HSA and 9275 non-HSA) and 43,200 matched traditional plan controls with bipolar illness (1:4 matching). Our smallest HDHP subgroups examined for primary outcomes will include 1525 HSA members (smallest medication adherence cohort) and 2160 non-white members (smallest emergency department and hospitalization outcome cohort).

For interrupted time series analyses of medication adherence, based on assumptions including 12 months of follow-up, autocorrelation of less than 0.3, and 0.05 type I error,¹³² we will have greater than 90% power to detect a 6% relative decrease in adherence in our smallest medication outcome subgroup (HSA-HDHP members). For example, we could detect an adherence rate change from 49% (as seen in previous literature¹³³) to 46% with a standard deviation of 1.5%. This is a *smaller* change in adherence than has been observed previously in HDHP-HSA studies.⁵⁷

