Differential dropout: Because vulnerable populations such as those with low SES might choose to forego employer health insurance coverage when offered only an HDHP, we will analyze whether differential dropout by group occurred after employer-mandated coverage changes. We will minimize its potential impact on our analyses by performing individual-level propensity matching based on multiple employee-level factors including SES to develop tightly-matched control groups. We will restrict our follow-up duration to 12 months because differential dropout from HDHPs could become more pronounced after the first enrollment year. We expect that we will be able to detect even small changes in utilization soon after the HDHP switch among our very large sample (Section C.10), so that 12 months should be sufficient follow-up to generate policy-relevant insights.

Financial incentives: We will also be unable to track amounts in Health Savings or Health Reimbursement Accounts because these data are only available from employers or financial institutions. This could lead to uncertainty regarding members’ financial incentives or disincentives to seek care. However, the presence of these accounts would bias results toward the null, so that any differences detected are likely to be robust.

Identification of clinical cohort: We will use claims data to identify bipolar disorder. Structured clinical interviews are the gold standard for identifying bipolar illness with high accuracy and inter-rater reliability. Enrollees misdiagnosed as *not having* bipolar disorder (i.e., false negatives) will not be in our cohort and we will be unable to comment on the impact of HDHPs in this group. However, several studies have demonstrated that administrative data can be highly accurate in establishing bipolar disorder for quality assessment, finding that among those identified as having bipolar disorder, 94% are confirmed by chart review.^{66,92,93}

Generalizability: Our inclusion criteria require traditional plan membership for at least a year at baseline, making our results applicable largely to health plan members familiar with the general structure of traditional insurance benefits. This limits generalizability of our results to populations such as previously uninsured low income employees who enter HDHPs. However, given the substantial percentage of employers that are

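### The 24-month enrollment rule selects members on staying enrolled for a year after the switch; baseline matching addresses only leaving explained by measured baseline factors, and no planned analysis addresses the rest

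*Combined protocol and SAP*

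**What the plan says.** Section C.4 sets the window, "We will follow all subjects for 1 year before and 1 year after the index month of switching", and the condition, "We will require continuous enrollment for the 24 month study period for both groups". Two other sections treat the same span as an entry criterion. Section C.5 reports that "we found 18,184,556 have a 2-year enrollment span, a study inclusion criterion". Section C.10 counts members who "met our inclusion criteria of 2 years continuous enrollment, with the first year in a traditional plan" and whose second year, in a traditional plan or an HDHP, is the follow-up year. The timeline in section D identifies eligible members in months 1-6 and matches them in months 7-12, so matching follows the enrollment filter.

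The Differential dropout paragraph of the limitations section says that vulnerable members, low SES being its example, "might choose to forego employer health insurance coverage when offered only an HDHP". It gives three responses:

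- a diagnostic: "we will analyze whether differential dropout by group occurred after employer-mandated coverage changes";
- a remedy: "We will minimize its potential impact on our analyses by performing individual-level propensity matching based on multiple employee-level factors including SES";
- follow-up limited to 12 months, because differential dropout may grow after the first year.

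Section C.9 adds a comparison of the analytic population with excluded members who have bipolar disorder. The matching variables in sections C.6 and C.8 are all measured at baseline and include the baseline outcome. The missing-data methods in C.8 concern SES variables. No section censors, weights or bounds for members who leave, and none gives a rule for deaths.

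**The concern.** Remaining enrolled for a year after the switch happens after exposure, and the plan itself expects exposure to affect it. A member who leaves or dies in that year is removed together with any hospitalization or ED visit that came first. If leaving is related to the outcome and differs between arms, the retained arms differ even when the switch has no effect.

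Aim 2 is the most exposed, because it asks whether HDHPs change adverse events. If sicker members leave the HDHP arm in excess, the artifact is a fall in hospitalization. That is the same direction as the decrease used in the power calculation, so it could be read as a real effect. The low-SES subgroup is also exposed, since the plan names those members as likely to leave.

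**Working it through.** **1. The plan's own figure.** Section C.10 gives 2160 HDHP members, 8640 controls, a baseline psychiatric hospitalization rate of 10%, type I error 0.05, 80% power and a detectable fall to 8%. I assume a two-sided test and read the correlation of 1 as one effective observation per person. With k = 4 controls per HDHP member, the pooled rate is (0.08 + 4 × 0.10)/5 = 0.096, and

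n = [1.960 × √(1.25 × 0.096 × 0.904) + 0.842 × √(0.08 × 0.92 + 0.10 × 0.90/4)]² / 0.02² = 2055.

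With continuity correction n = 2117. Power at 2160/8640 is 82.0%, and the decrease detectable at 80% power is 19.5%. The stated 20% reproduces and serves as the yardstick below.

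**2. Unmatched illustration.** The documents give no disenrollment or death rates, so e and q are assumptions. Let e be the excess proportion leaving the HDHP arm and q their follow-up hospitalization risk, with 10% risk overall and no true effect. The retained HDHP rate is (0.10 − e·q)/(1 − e).

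| e | q | Retained rate | Relative change |
|---|---|---|---|
| 2% | 20% | 0.096/0.98 = 9.80% | −2.0% |
| 5% | 20% | 0.090/0.95 = 9.47% | −5.3% |
| 5% | 30% | 0.085/0.95 = 8.95% | −10.5% |
| 8% | 30% | 0.076/0.92 = 8.26% | −17.4% |

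The sign depends on who leaves. In the opposite extreme, where leavers would have had no events (q = 0), the retained rate is 0.10/0.98 = 10.20% (+2.0%) at e = 2% and 0.10/0.92 = 10.87% (+8.7%) at e = 8%.

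**3. A second route.** Let r be the probability of staying for HDHP members who would be hospitalized, divided by that for those who would not, with r = 1 in controls. With no true effect the observed HDHP rate is 0.10r/(0.10r + 0.90).

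- r = 0.95 gives 9.55% (−4.5%).
- r = 0.90 gives 9.09% (−9.1%).
- r = 0.783 gives 8.00%, the whole detectable effect.

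For a simple comparison of follow-up proportions at r = 0.90, the chance of a false significant result is 24% with 2160/8640 and 82% with the full 10,800/43,200. A true rise from 10% to 12% is hidden when 0.12r/(0.12r + 0.88) = 0.10, that is at r = 0.815.

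**4. What matching does.** I simulated 20 million members with no true effect, 20% of them HDHP. A measured baseline factor and an unmeasured frailty each had 30% prevalence. Annual risk was 5.5%, plus 5 points with the measured factor and 10 points with frailty. Everyone had a 5% chance of leaving, and HDHP members had 15 points more if they carried the named characteristic. Retained members were matched exactly on the measured factor and the baseline outcome. Post-switch differences, in percentage points:

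| Excess leaving depends on | Leaving, HDHP vs control | Before matching | After matching |
|---|---|---|---|
| measured baseline factor | 9.5% vs 5.0% | −0.16 | 0.01 |
| unmeasured frailty | 9.5% vs 5.0% | −0.36 | −0.35 |
| the post-switch event | 6.5% vs 5.0% | −1.44 | −1.43 |

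Because matching equalizes the baseline outcome, the matched difference-in-differences equals the last column. The third row agrees with step 3: r = 0.80/0.95 = 0.842 gives 0.0842/0.9842 = 8.56%, a difference of −1.44 points.

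**The case against.** The best defense is that the plan names a mechanism that matching can handle. Its example is low SES, which is measured at individual level and enters the match along with prior use, expenditure and the baseline outcome. The first simulated case supports this. A reader might infer that matching among stayers does nothing about dropout; the documents do not support that.

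The plan also discloses the problem and has more safeguards than the dropout check. The 12-month limit was chosen for this reason, and the comparison with excluded members is aimed at selection from the enrollment criteria. These deserve credit, but they limit or describe the problem and correct no estimate. The dropout analysis has no stated method, threshold or consequence.

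A reader might also infer that the worst outcomes are missing from the HDHP arm and that Aim 2 is therefore biased toward no harm. The documents give no disenrollment rates, deaths or reasons for leaving. The rule binds both arms, so job loss or death matters only where it differs between them, and step 2 shows the sign reversing if low-risk members leave.

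The 2-17% range uses neither the match nor the pre-period of the planned difference-in-differences, so it is not an estimate of that estimator's bias. Any part of the leavers' extra risk that matched covariates capture would drop out. In the frailty case, difference-in-differences among retained members without matching was about zero, because frailty acted equally in both years; the −0.35 points appear once the baseline outcome is matched. Leaving that depends on the post-switch event is not rescued either way (−1.39 points unmatched, −1.43 matched).

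Finally, a closed cohort is a coherent choice for effects among continuously insured members, and person-time suits some outcomes poorly: annual cost under an annual deductible, and laboratory tests counted per year or half-year. This is a good reason to confine the remedy to Aim 2 events.

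**Conclusion.** The concern holds in a limited form. The enrollment rule conditions on a post-switch event that the plan expects exposure to influence. Matching can balance the part explained by measured baseline variables, for stayers only. It cannot correct leaving driven by unmeasured severity or by what happens after the switch, including death, and no other planned analysis does so. The claim that matching will minimize the impact therefore goes further than the method allows.

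Neither size nor direction can be fixed from the documents. The spurious decrease of 2-17% rests on assumed excess leaving of 2-8%, an assumed risk of 20-30% among leavers, no true effect and no matching. It shows that plausible-looking values can reach a material share of the 20% detectable effect. This does not invalidate the primary design; it calls for a sensitivity analysis and a narrower claim.

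**What to change.** Keep the 24-month cohort as primary and state that its estimates apply to continuously enrolled members. Pre-specify one sensitivity analysis for the Aim 2 ED and hospitalization outcomes:

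- Define the cohort by 12 months of baseline enrollment plus enrollment in the index month, and match at that point.
- Follow to disenrollment, death where identifiable, or month 12, using person-time.
- Weight by the inverse probability of remaining enrolled. The weights can use claims after the switch, which baseline matching cannot.
- Report leavers by arm, including those who leave at the switch itself, whom an index-month cohort still misses.
- Add simple bounds over a stated range of event rates among leavers, because the weights also rely on measured predictors.

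In the Differential dropout paragraph, say that matching addresses only dropout explained by measured baseline factors.

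The cost is extra programming on claims that the plan says will be held in-house, and partial follow-up for some members in this analysis. It is a cheap improvement. Extending person-time to the annual cost and laboratory-monitoring outcomes would be a debatable trade-off and is not proposed.

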B.3. Pathways toward Improvements in Care [RQ-3]: HDHPs could cause disruptions in treatment of bipolar illness due to cost-related nonadherence or confusion about coverage details. HDHPs could also cause reductions in outpatient and inpatient care, or increased psychiatric hospitalizations due to treatment disruptions. Because of the rapid growth in HDHPs, our study is highly relevant to policymakers at all levels. Both types of HDHPs (with and without medications subject to the deductible) as well as traditional plans with no deductible are all highly prevalent in the US. This wide “practice variation” in insurance benefits design implies a crucial need to understand the impacts of design differences in order to optimize patient health. Prior research indicates that even small differences in insurance design can have powerful consequences for vulnerable patients.

Opportunities to implement policy recommendations would be readily available. Insurers redesign benefit offerings every year and respond quickly to shifting pressures from employers. Our study potentially includes an immediately-available “policy intervention,” if HDHPs with generous medication coverage promote bipolar medication adherence and better health outcomes, employers and health insurers could quickly shift to such designs. Evidence that exempting mood stabilizing drugs from full cost-sharing preserves appropriate utilization could also contribute to amendments to the 2003 Medicare Modernization Act that requires HSA-eligible HDHPs to subject all medications to the deductible.²⁴ State and federal regulators closely examine insurer practices and set standards for benefits packages. We expect that policy makers will use our results to introduce health plan designs that promote high quality care among patients with mental illness.

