
Subgroups [IRQ-4]: We will stratify our analyses by additional characteristics to permit evaluation of vulnerable subgroups: comorbidity level (e.g., highest tertile versus intermediate and lowest tertiles of validated Adjusted Clinical Groups score^{94,95}), SES (e.g., highest versus lowest tertile household income), rural versus urban residency, and race/ethnicity group¹⁵²⁻¹⁵³(non-Hispanic white versus black, Asian, Hispanic, and other). These variables are described in section C.8. For Rural versus non-rural areas; non-rural areas will be the reference group. We will use Rural-Urban Commuting Area (RUCA) codes that reflect travel and shopping patterns at the county level. Using an established probabilistic ZIP code-to-county file,¹⁴⁸ we will assign patients by their residential ZIP codes to RUCA groups. Similar to previous research,¹⁴⁹⁻¹⁵¹ we will categorize the 10-point RUCA classification into: “rural” (RUCA codes 7-10) and “non-rural”, comprising large rural cities/towns (RUCA codes 2-6) and urban areas (RUCA code 1).

C.6 Matching Strategy for Aims 1-3 [CI-5]: For comparing effects among insurance designs, we will use propensity score matching based on both employer- and member-level characteristics to balance the study and control groups on observed characteristics as in our prior work.⁹⁶⁻⁹⁸ We will first match similar employers (to minimize employer selection effects) and then match individuals within groups of similar employers to ensure high comparability between study groups. The individual match will include matching on the baseline outcome measure, an approach crucial to generating estimates comparable to randomized controlled trials.^{77,85}

[name]

We will use the sample selected with this method for interrupted time-series analyses and for pre-post with comparison group difference-in-differences (Section C.9). Use of comparison groups matched at both the employer- and individual-level will increase comparability between HDHP and traditional plan cohorts in baseline employer characteristics, member demographic characteristics, and baseline health care utilization. This offers a further degree of control for any potential contemporaneous changes that may influence specific study outcomes.^{41-44,54,55,80,99}

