treatment with a particular medication (e.g., proportion of days covered by a mood-stabilizing agent).^{89,90,110}

(iv) **Guideline-recommended clinical monitoring:** The American Psychiatric Association¹⁴ recommends routine drug level monitoring for a number of bipolar disorder medications. Our quality measures will include: for lithium, carbamazepine and valproate users: testing for drug serum level at least once in a year;¹¹¹ for lithium users: renal and thyroid function tests every 6 months; and for valproate and carbamazepine users: blood counts and hepatic function tests every 6 months.^{14,111} In addition, use of 2nd generation antipsychotics may be associated with cardiometabolic risk through effects on body weight, and lipid and glucose metabolism.^{112,113} Consensus guidelines recommend that patients receiving 2nd generation antipsychotics be monitored for lipid and glucose levels every 3 months to ascertain risk of diabetes and cardiovascular disease.¹¹⁴ Thus, we will also assess lipid (total cholesterol and triglycerides) and serum glucose testing every 6 months in users of these medications, as in previous research.¹⁰⁸

(Aim 2) Adverse Patient Clinical Outcomes: We will examine changes in rates of: (i) psychiatric and non-psychiatric ED visits and day hospitalizations to determine if cost-sharing under HDHPs resulted in adverse short-term health events among patients with bipolar disorder, and (ii) psychiatric and non-psychiatric hospitalizations and hospitalization days as evidence of the impact of HDHPs on overall rates of serious morbidity. As in our prior work, we will define psychiatric-related events as those associated with a primary diagnosis of bipolar disorder (ICD-9: 296.0, 296.1, 296.4-296.8, 301.11 and 301.13^{43-45,90}), depression (ICD-9: 296.2, 296.3, 298.0, 300.4, 309.1, and 311⁴²), or schizophrenia (ICD-9: 295^{36,41}), substance abuse (ICD-9: 291, 292, 303-305.0, 305.2-305.7, 305.9¹⁰⁹), or events in psychiatric hospitals.⁴⁵

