Member-level Covariates include: bipolar disorder type, age, sex, SES, race/ethnicity, state of residence, rurality, Dartmouth Atlas Hospital Referral Region of residence, baseline out-of-pocket and health plan expenditures, number and month (relative to index date) of outpatient/ED/hospital visits, and enrollment in individual versus family coverage. To derive indicators of race/ethnicity, we will first use a variable supplied by the data vendor that applies surname analysis to categorize members as Hispanic or Asian. We will then use US Census block group data¹¹⁶ (geocoding) to indicate predominantly black or white neighborhoods. We will combine both techniques because geocoding is not sensitive in detecting ethnicity¹¹⁷ and surname analysis is non-informative regarding race. **[MD-2]** This validated approach has a high positive predictive value.¹¹⁸⁻¹²² We will have access to individual-level Credit Report-derived variables for income and net worth, which is a major advance over previous studies that used only neighborhood SES measures. We will also determine neighborhood SES (geocoded poverty and education levels) and use principal components approach to calculate a neighborhood SES index.^{99,123,124,125} Adjusted Clinical Groups scores^{94,95} will estimate comorbidity.

[name]

To account for SES variables' data missingness among HDHP and traditional plan adult members, we will use 3 methods to accommodate missingness: (a) multiple imputation, (b) modeling missingness as a member-level characteristic, and (c) excluding members with missing data. If findings differ, we will present results using all 3 methods in manuscripts or attached appendices. We will use SAS procedures PROC MI and PROC MIANALYZE to impute the missing individual level covariates and conduct the statistical analyses under the assumption of missing at random. The SAS procedure PROC MI will impute the missing variables (including individual net worth, income level, poverty level and education level) using other available variables such as age, gender, census block level income, poverty, education and etc. Then we will use PROC MIANALYZE to analyze the imputed data. We will also explore certain Bayesian imputation techniques to handle missing data in case missing is not at random and compare the results.^{146,147}

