C.9 Analysis Plan for Aims 1-3 [IR-3; HT-1 to HT-4]: Overview: These analyses will determine how specific outcomes change after employer-mandated switching from traditional plans to HDHPs. To address methodological standard IR-3, we plan to use the most rigorous quasi-experimental retrospective longitudinal designs and analyses available for AIMS 1-3, namely interrupted time series with comparison series matched on multiple baseline covariates as well as the baseline trend of outcome measures. For Aim 4 we will use appropriate standard techniques for qualitative analyses of interview data (detailed below). We will first compare the characteristics of our matched cohorts (HSA-eligible and HSA-ineligible HDHP members, and traditional plan controls) using chi-square tests, t-tests and Poisson or quantile regression.¹²⁶ We will contrast sociodemographic characteristics, employer characteristics, and baseline health care utilization. Subsequent analyses will use time-series plots and rigorous analytical methods appropriate for each outcome, described below. Data collected on the same individuals in successive years are correlated (“repeated observations”). The extended general linear models—generalized estimating equations (GEE) and generalized linear mixed models (GLMM) for binary, count, or continuous measured outcomes—are appropriate methods for estimating parameters to adjust for these correlations within subjects.^{82,83} The term of interest in our GEE or GLMM models will be the interaction between *time* (pre versus post) and *cohort* (HDHP versus traditional plan). Statistical analyses in Aims 1-3 will first compare those transitioning to HDHPs with patients remaining in traditional plans; then contrast effects between HDHP members with full drug cost-sharing (HSA-eligible plans) and those transitioning to HDHPs without full drug cost-sharing (HSA-ineligible HDHPs). Each HDHP group will have as controls only those traditional plan members paired to a given HDHP member during the propensity score match. To examine possible selection effects due to applying our enrollment criteria and propensity matching approaches (see C.10), we will also compare our analytic population to members with bipolar disorder who were excluded from the sample.^[MD-4; CI-2]

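### C.5 sets no window for the qualifying bipolar diagnosis, so members appear able to enter the main cohort through follow-up-year care that is itself an outcome

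*Combined protocol and SAP*

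**What the plan says.** C.5 (Inclusion Criteria) identifies cases as members with "at least two ambulatory encounters or one hospital encounter with a diagnosis of bipolar disorder". It ties age to the start of the baseline period but gives the diagnosis rule no date. The cohort count starts from members with a two-year enrollment span: "Among these, 148,706 have at least 1 inpatient or 2 outpatient diagnoses of bipolar disorder". The same section then plans a variation: "We will conduct sensitivity analyses of our main results varying our bipolar diagnosis criteria [e.g., requiring diagnosis prior to index date".

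On outcomes, C.7 (Aim 1) counts total outpatient visits and also mental health visits, using ICD-9 290-310 among other codes. C.7 (Aim 2) counts psychiatric and non-psychiatric admissions, and for the psychiatric ones "we will define psychiatric-related events as those associated with a primary diagnosis of bipolar disorder", among other conditions. B.3 states the expected effect of the exposure: "HDHPs could also cause reductions in outpatient and inpatient care, or increased psychiatric hospitalizations due to treatment disruptions".

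Three other provisions bear on the point. C.6 says "The individual match will include matching on the baseline outcome measure". C.8 lists "number and month (relative to index date) of outpatient/ED/hospital visits" and bipolar type among the member-level covariates. C.9 adds that "we will also compare our analytic population to members with bipolar disorder who were excluded from the sample".

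**The concern.** A member who first meets the diagnosis rule in the follow-up year must have had at least one bipolar-coded encounter in that year, in either arm. In that group an HDHP cannot be seen to remove such care altogether, because anyone whose care was removed is not in the cohort.

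C.5 makes this concrete by excluding patients with a single outpatient bipolar diagnosis. Take a member with one bipolar visit before the switch and none earlier. If a second visit follows the switch, the member is in. If cost-sharing deters that visit, the member is out. The cohort could therefore lose the patients whose forgone care Aim 1 is meant to detect.

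For Aim 2, if an HDHP lowers outpatient diagnosis, the HDHP arm's late entrants contain relatively more people who came in through an admission. Psychiatric hospitalization can then appear to rise with no true effect.

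The same gap affects bipolar type, which would be a post-exposure matching variable for late qualifiers, and the schizophrenia and schizoaffective exclusion, whose window is also not stated.

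**Working it through.** **Is there a window anywhere?** C.4 sets 12 months before and 12 months after the index month. C.5 dates age but not diagnosis. C.6, C.8, C.9, C.10 and the limitations section add no diagnosis window. If the main analysis already required a pre-index diagnosis, listing that requirement as a variation would be pointless. Follow-up-year entry is therefore an inference, but a strong one.

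**Do entry encounters overlap outcomes?** The entry codes (296.x, 301.11, 301.13) lie within 290-310. Any qualifying visit is at least a total outpatient visit. Any qualifying admission is either a psychiatric or a non-psychiatric admission.

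**The plan's own figure.** C.10 gives 2160 versus 8640, 10% versus 8%, type I error 0.05 and 80% power. For a two-sided two-proportion z-test, the pooled rate is (0.08 + 4×0.10)/5 = 0.096, the null SE 0.00709 and the alternative SE 0.00667. Then z = (0.02 − 1.96×0.00709)/0.00667 = 0.916, so power is 82.0%. The relative decrease detectable at 80% power is 19.5%, which agrees with the stated 20%.

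**Illustration of the bias.** Only the 10% hospitalization rate comes from the documents (C.10). The assumptions are:
- late entrants are a share s = 0.10-0.30 of both arms;
- an undiagnosed case qualifies by admission with probability h = 0.05-0.10;
- it qualifies by outpatient visits with probability o = 0.30-0.60;
- the HDHP multiplies the affected route(s) by 0.8.

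The probability that a late entrant was admitted is h/[1 − (1−h)(1−o)]. The arm rate is (1−s)×(established members' rate) + s×(late-entrant rate). The established rate is 0.10, or 0.08 in the HDHP arm where admissions fall.

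With h = 0.10 and o = 0.30, the late-entrant rates are:
- control: 0.10/0.37 = 0.270
- HDHP, both routes reduced: 0.08/0.3008 = 0.266
- HDHP, admissions only: 0.08/0.356 = 0.225
- HDHP, outpatient only: 0.10/0.316 = 0.316

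| s | control | both routes (RR) | admissions only (RR) | outpatient only (RR) |
|---|---|---|---|---|
| 0.10 | 0.1170 | 0.0986 (0.843) | 0.0945 (0.807) | 0.1216 (1.039) |
| 0.30 | 0.1511 | 0.1358 (0.899) | 0.1234 (0.817) | 0.1649 (1.092) |
| true RR | | 0.80 | 0.80 | 1.00 |

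Over the full grid the estimated risk ratios are 0.82-0.90, 0.80-0.82 and 1.02-1.09. On the absolute scale the distortion can go either way. At s = 0.30 the both-routes difference is 0.1358 − 0.1511 = −1.5 points and the admissions-only difference is 0.1234 − 0.1511 = −2.8 points, against −2.0 in established members.

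**Unequal shares.** If matching does not equalize the late-entrant share, the HDHP share becomes s·r/(1 − s + s·r), where r is the ratio of qualifying probabilities (HDHP/control). For example, take h = 0.05, o = 0.60, s = 0.30, outpatient only. Then r = 0.506/0.62 = 0.816 and the HDHP share is 0.259. The rates are 0.0997 and 0.0942, giving RR 1.06. Over the grid the ranges become 0.82-0.85, 0.80-0.81 and 1.02-1.06.

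**Power after restricting to pre-index diagnoses** (same test, assumed late-entrant shares):

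| share removed | n per arm | power, 10% vs 8% | relative decrease detectable at 80% |
|---|---|---|---|
| 0% | 2160/8640 | 82.0% | 19.5% |
| 10% | 1944/7776 | 77.7% | 20.5% |
| 20% | 1728/6912 | 72.6% | 21.7% |
| 30% | 1512/6048 | 66.5% | 23.2% |

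**The case against.** The plan never says outright that follow-up diagnoses count. The image of Figure 3 and the cited diagnosis algorithm could not be read, and C.5 describes the intervention cohort as traditional-plan members with bipolar illness who then switch, which suggests prior illness. That is why the finding is put as an inference. The description is not a timing rule, however, and no readable text supplies one.

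The pre-index analysis is already listed, so the correction could be called a relabelling. But it is given only as an example, and nothing says which result stands if the two disagree. The comparison with excluded members describes selection without correcting the estimate. Matching on baseline outcome and visit timing may partly balance the share of late entrants. It cannot undo selection on events after the switch.

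The overlap is also partial. Entry accepts a bipolar code in any position, whereas psychiatric events mostly require a primary diagnosis, so using one h for both is a simplification. Adherence and laboratory monitoring are not entry encounters, and no effect on them is shown here.

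Finally, the upper ends of the ranges depend on equal late-entrant shares. Letting the shares differ brings 0.90 down to 0.85 and 1.09 down to 1.06. The direction does not change. If the HDHP affects neither route to diagnosis, there is no bias.

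**Conclusion.** The concern holds and should be fixed; confidence is medium, because follow-up-year entry is inferred. As written, the primary analysis appears to condition entry on post-switch care that the plan itself expects the exposure to change. Size and sign cannot be determined, since the documents do not split the cohort by timing of diagnosis. The illustrations run from negligible (only admissions fall) through attenuation of a real decrease to a spurious rise of 2-9% in hospitalization (2-6% with unequal shares). All inputs except the 10% rate are assumptions. A false increase in psychiatric hospitalization would bear directly on the main Aim 2 conclusion, so this is more than a missing detail.

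**What to change.** - In the primary cohort, require the one inpatient or two outpatient bipolar diagnoses before the index date.
- Take bipolar type and the schizophrenia/schizoaffective exclusion from the same pre-index window.
- Make the any-time definition the sensitivity analysis, and state that the pre-index result governs.
- Report by arm, before and after matching, how many members qualify only after index.
- Restate C.10 for the resulting cohort. Its counts start from members with one or more bipolar diagnoses, not from the current rule.

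No new data are needed, only a recount, a rematch and a revised power statement. The costs are that newly diagnosed members drop out and precision falls; under the assumed 10-30% share, the smallest Aim 2 subgroup would fall below the stated 80% power. If a pre-index window was always intended, one sentence in C.5 saying so resolves the main point, and the listed sensitivity analysis should then be reworded.
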